18.3 DATA MAINTENANCE AND RETENTION

It is the responsibility of the site investigator to maintain, in an exhaustive and centralized manner, a system for collecting all the relevant information.

Investigators will be informed that they should keep all study records in a safe place and with limited access during a period of ten years or more according to the applicable current regulations.

Investigators will be informed that before eliminating any study data/ document, they have to consult it with the Sponsor, as well as to notify in writing any change in location, availability or custody of the study files.

18.4 DATA MANAGEMENT

18.4.1 Data capture through Individual Clinical Record Form (ICRF)

18.4.1.1 Data capture

The sponsor will provide each study site with a printed copy of the reference template for data capture (ICRF) in carbonless paper or digital form, sending a copy to the site and another to the sponsor.

Data entry at the site will be made by the investigator, study coordinator or other study staff properly trained and designated.

The ICRFs are used to keep the study data and are an integral part of the study and subsequent reports. Therefore, the ICRFs must be completed for each patient recruited in accordance with the source data of the patient at every visit.

Patients should not be identified by the name. An appropriate coded identification will be used so that they cannot be identified (if applicable). The site investigator should maintain a separate form with the names of the patients, the non - identifying initials (if applicable) and the addresses of the patients (a patient identification form).

Each completed ICRF must be verified by the site investigator at each visit and should be contrasted with the source documents of the patient by the clinical trial monitor. Each entry must be monitored by the monitor and by the staff from the *Procesamiento de Datos* department (DM).

18.4.1.2 Discrepancy Management

The internal consistency and the integrity of the data entered in the study database are defined by a series of validations. A deviation from these predefined and automated validations, may create an inconsistency in the database that can be resolved by using a data correction form.

There are 2 main types of discrepancies:

- Automatic discrepancies automatically generated during data entry or following data logical execution.
- Manual discrepancies, that can be generated by a system user at any time.

It will be the responsibility of the investigator and his team to resolve any data discrepancy in due time and manner. The study monitors will perform the follow - up to confirm that these discrepancies are resolved.

18.5 ADDITIONAL DOCUMENTS AND RECORDS

- 1) Patient selection and allocation form: A list of all patients who have signed the informed consent and that have been selected.
- 2) Patient identification form: Allows the investigator to associate the selected patient with the study. This information will include, but will not be limited to only: patient name, date of birth, contact information and non - identifying patient initials (if applicable). This confidential list must be kept at the research site and will not be sent to the sponsor.
- 3) Drug accountability form: This form reflects the total amount of study drug that has been dispensed and returned by each patient in the relevant study visits.

19 QUALITY ASSURANCE AUDITS

19.1 QUALITY ASSURANCE PROGRAM

This clinical trial can be audited in accordance with the Quality Assurance (QA) Program of the sponsor.

The purpose of these audits is to determine if this study is being conducted or monitored in accordance with both the Protocol, and with the GCP guidelines and local regulations. These audits will also increase the credibility of the study data, so that any type of study documentation may be required by any regulatory authority for inspection. These audits, if performed, will be scheduled with the site and will be carried out in a reasonable period of time.

19.2 REGULATORY INSPECTIONS AND AUDITS

The study may be inspected by regulatory agencies and audited by ethics committees. These inspections/ audits will take place at any time during or after the study and will be performed in accordance with the national regulations as well as the ICH guidelines.

20 STUDY MONITORING

20.1 MONITORS AND MONITORING VISITS

The study monitor will be responsible for ensuring compliance with the current Good Clinical Practice guidelines, the ICH guidelines and the standard operating procedures of the sponsor or designee. The study monitors will be designated by the sponsor. The monitors will observe the current Good Clinical Practice guidelines, the ICH guidelines and the standard operating procedures of the sponsor or designee.

Regular monitoring of the study data in accordance with the specific study monitoring plan will be conducted. Individual sites will be monitored to check the pace of recruitment, data and protocol compliance. The frequency of monitoring of individual sites may depend on the pace of recruitment, the quantity of data collected and the complexity of the study, variables that will be documented in the monitoring plan.

These monitoring visits will be carried out with the purpose of verifying the protocol compliance as well as the accuracy of the data and that these are collected in the ICRF. The study monitor will verify the entries in the ICRF comparing them with the main source of information (hospital/ clinic/ official records), which must be available for this purpose. The monitor will review the maintenance of official documentation and the study medication accountability. The monitor will periodically review study progress along with the site investigator and the other people participating in the study. At study end, there will be a monitoring closure visit. Monitoring visits will be scheduled in advance with the site staff by mutual agreement and at an acceptable time for both. The site staff should provide sufficient time to the monitor for the review of the ICRFs as well as of the source documents. The coordinator and/ or investigator will answer any question or provide any clarification in relation to the data. The site investigator must provide a place and a time suitable for those visits to be performed.

20.2 MAIN SOURCE DOCUMENTS

The investigator should retain the primary documentation sources for data entry in the ICRF. These documents, considered as "source documents", should include, but will not be limited to:

- Anthropometric and demographic information.
- Evidence that supports the diagnosis/ condition for which the patient is being studied.
- General information to support patient participation in the study.
- Medical information and physical examination findings.
- Records of hospitalizations or emergency visits (if applicable).
- Each study visit must be dated including any relevant finding/ note found by the investigator; occurrence (or absence) of adverse events, as well as changes in the use of the medication, including the start and end date of drug administration.
- Any additional visit during the study.
- Any relevant telephone conversation with the patient related to the study or to a possible adverse event.
 - The original informed consent form signed for study participation.

The investigator must also keep all those printed documents/ test/ procedure reports performed that are requested in this study. During the monitoring visits, the monitor will need to verify the ICRF data, comparing them with the source information.

21 USE OF INFORMATION AND DATA PUBLICATION

All information provided by the sponsor in connection with this study, which has not been previously

published, is considered confidential information. This information includes, but is not limited to, the Investigator's Brochure (if applicable), clinical protocol, data capture notebooks and other scientific data. Any data collected during the study are also considered confidential. This confidential information will remain the exclusive property of the sponsor, it will not be disclosed to third parties without the written consent of the sponsor, and it will not be used for other purposes than study conduct.

The information developed during the conduct of this clinical study is also considered confidential and will be used by the sponsor in connection with the development of the drug. The information must be disclosed as considered by the sponsor. To allow the use of information derived from this clinical trial, the investigator is obliged to provide the sponsor with the complete results and all data developed in this study. The information obtained during this study may be available for other investigators who are conducting similar studies.

If the investigator wishes to publish the data from this study, he must deliver a manuscript to the sponsor for review 60 (sixty) days before its publication. In the event that the sponsor chooses to publish this study data, it will deliver a copy to the investigator at least 30 days before the presumed date of delivery to the defined editor. Any publication resulting from this research should include the investigators who participated on behalf of the sites and Biosidus, according to the usual criteria of authorship of scientific publications set forth in the Uniform Requirements for Manuscripts submitted to biomedical journals: Writing and editing for biomedical publication, from the International Committee of Medical Journal Editors.

The sponsor maintains the right to eliminate the confidential information from the manuscript and may make any objection to or suggestion regarding its publication and/ or the time of the publication (at the sponsor's full discretion).

22 SITE STAFF

22.1 RESEARCH SITE

The staff from each research site will consist at least of a Principal Investigator and a clinical study coordinator or sub-investigator.

22.2 PRINCIPAL INVESTIGATOR

At each research site, a physician will be designated to act as Principal Investigator and will bear overall responsibility for the management of the team of the site where the study will be conducted and for the study aspects at the appropriate site. The Principal Investigator will supervise the recruitment of patients, the correct conduct of the trial in accordance with the protocol and the requested data capture.

22.3 STUDY COORDINATOR OR SUBINVESTIGATOR

The study coordinator or sub-investigator will be appointed by the Principal Investigator and will be responsible for assisting the principal investigator in all those tasks that have been delegated to him.

23 SPONSOR

23.1 BIOSTATISTICS, DATABASE AND PROGRAMMING

The departments of Biostatistics, Database and Programming are responsible for the proper use of the data management application, of the completion of the common data management procedures and statistical analysis, as detailed in this Protocol. All procedures will be carried out in accordance with the local and ICH guidelines.

Based on the sponsor criterion, the biostatistics, database and programming tasks can be performed by a CRO.

23.2 CLINICAL MANAGEMENT

The local *Gerenciamiento Clinico* department (project leader or manager) is responsible for the daily activities of the local study and for ensuring that the sites and the Sponsor comply with all applicable regulations related to the clinical research.

Based on the sponsor criterion, this task can be performed by a CRO.

23.3 MONITOR

The monitor is responsible for monitoring the study in the participating sites. Monitoring visits will be agreed in advance and by mutual agreement at a time acceptable to both the monitor and the site staff. Based on the sponsor criterion, this task can be performed by a CRO.

23.4 MEDICAL MONITOR

The Medical Monitor will be responsible for the periodic review of the clinical safety data and for the resolution of study - related medical issues.

MDRD	Modification of Diet in Renal Disease Study
MedDRA	Medical Dictionary For Regulatory Authorities
min	minute
ml	mililiter
SAP	Statistical Analysis Plan
SPSS	Statistical Package for Social Sciences
"t"	Student test
TEAE	treatment - emergent adverse event
TIA	Transient Ischemic Attack

3 Introduction

3.1 Purpose of the analyses

These analyses will assess the efficacy and safety of HEMAX PFS® versus in comparison with EPREX/ ERYPO®.

3.2 Key Protocol Information

3.2.1 Study Objectives and Endpoints

3.2.2 Study Objectives

GENERAL OBJECTIVE

Evaluate the efficacy and safety of HEMAX PFS compared with EPREX/ERYPO®, following a dose titration and maintenance scheme similar to that used in the clinical practice in Argentina.

PRIMARY OBJECTIVE:

Evaluate the efficacy of treatment with epoetin alfa through increased levels of hemoglobin (Hb) from baseline value to the mean value of the 8 to 12 weeks of treatment, comparing patients treated with HEMAX PFS versus those treated with EPREX/ ERYPO®.

Evaluate the safety through the incidence of adverse events and adverse reactions after 12 and 24 weeks of treatment, comparing patients treated with HEMAX PFS versus those treated with EPREX/ ERYPO.

SECONDARY OBJECTIVES:

Evaluate the efficacy of treatment with epoetin alfa through the percentage of responder patients (increase of Hb \geq 1g/ dl) after 12 weeks of treatment, comparing patients treated with HEMAX PFS versus those treated with EPREX/ ERYPO®.

Evaluate the percentage of transfusion requirement after 12 weeks of treatment, comparing patients treated with HEMAX PFS versus those treated with EPREX/ ERYPO®.

Evaluate the intragroup efficacy (HEMAX PFS and EPREX/ ERYPO®) of treatment with epoetin alfa through increased levels of hemoglobin from baseline in each one of the intermediate visits until the week 12 visit.

Evaluate the intragroup efficacy (HEMAX PFS and EPREX/ ERYPO®) of the change from the twice-a-week dosing during the titration phase to a weekly dosing during the maintenance phase through the variation of the hemoglobin levels from week 12 to weeks 16, 20 and 24.

In addition, at week 12 and 24 visits, an anti-erythropoietin antibody dosing will be performed to evaluate treatment immunogenicity..

EXPLORATORY OBJECTIVE

Evaluate the baseline value of hepcidin through ELISA at 12 and 24 weeks, in relation to treatment response.

3.2.3 Endpoints

EFFICACY EVALUATION

The following parameters will be evaluated for treatment efficacy, according to the objectives defined by the protocol at each visit:

- Levels of hemoglobin and its variation at each visit, with intragroup and intergroup comparison

The primary efficacy assessment will be carried out through the levels of hemoglobin increase from baseline value to the mean value of the visits between week 8 and 12, comparing patients treated with HEMAX PFS versus those treated with EPREX/ ERYPO®.

- Percentage of responder patients, defined as the increase of Hb $\geq 1\text{g/ dl}$ without transfusion requirement.

Percentage of responder patients (increase of Hb $\geq 1\text{g/ dl}$) after 12 weeks of treatment, comparing patients treated with HEMAX PFS versus those treated with EPREX/ ERYPO®.

- Number and percentage of patients that require at least one transfusion.

Percentage of transfusion requirement after 12 weeks of treatment, comparing patients treated with HEMAX PFS versus those treated with EPREX/ ERYPO®.

- Intragroup efficacy of treatment with epoetin alfa

Increased levels of hemoglobin from baseline in each one of the intermediate visits until the week 12 visit.

- Intragroup efficacy of the change from the twice a week dosing during the titration phase to a weekly dosing during the maintenance phase.

Variation of the hemoglobin levels from week 12 to weeks 16, 20 and 24.

- Level of hepcidin at baseline, 12 and 24 weeks.

Relationship between the basal levels of hepcidin with the fall in filtrate and the hemoglobin level.

Response of hepcidin levels to treatment with erythropoietin

Association between hepcidin levels and the subgroup of patients who do not respond to erythropoietin.

SAFETY EVALUATION

- Adverse events:

Incidence of adverse events and adverse reactions will be evaluated after 12 and 24 weeks of treatment, comparing patients treated with HEMAX PFS versus those treated with EPREX/ ERYPO®.

In addition, and with focus on safety, the following will be discussed:

- Incidence of thromboembolic events (myocardial infarction, cerebrovascular accident, deep vein thrombosis and other thromboembolic events).
- Incidence of hypertension as TEAE.
- Blood pressure values at each visit.
- Complete baseline laboratory data and at week 12 and 24 visits,
- Antibody dosages, baseline and at weeks 12 and 24
- Vital signs: Determinations of pulse and blood pressure were recorded at every visit.
- Physical examination: A brief physical examination was carried out at the baseline visit (week 1).
- Electrocardiogram: An electrocardiogram was performed at the baseline visit (week 1).

3.2.4 Statistical Hypotheses

Treatment equivalence will be established if the difference between the two groups excludes a difference between treatment groups greater than 1g/ dl in hemoglobin increase from baseline value to the mean value of the visits between week 8 and 12 with a difference in the mean dose of epoetin alfa in these visits no greater than 20%.

The following equivalence statistical hypotheses is to be tested at a two-sided significance level of 5%:

- H0: Treatment difference in mean Hb during the primary efficacy evaluation period, between treatment arms (HEMAX PFS versus EPREX/ERYPO®), is within ± 1.0 g/dL or less.
- H1: Treatment difference in mean Hb during the primary efficacy evaluation period, between treatment arms (HEMAX PFS versus EPREX/ERYPO®), is greater than ± 1.0 g/dL.

Only when the primary endpoint achieves equivalence, statistical testing will progress to the secondary endpoints according to the stepdown procedure.

4 Study Methods

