13.5 INVESTIGATIONAL PRODUCT/ STUDY DRUGS DESCRIPTION

HEMAX PFS will be used in prefilled syringe in 1000 IU/ 0,5ml, 2000 IU/0,5ml, 3000 IU/0,3ml and 4000 UI/0,4ml presentations.

The sponsor Biosidus Argentina SA, is responsible for the manufacture of HEMAX PFS in accordance with the Good Manufacturing Practice (GMP) guidelines.

The solution for injection should be kept in the refrigerator, at a temperature between 2°C and 8°C.

EPREX/ ERYPO® injectable in prefilled syringe in 1000 IU/0,5ml, 2000 IU/0,5ml, 3000 IU/0,3ml and 4000 IU/0,4ml.presentations will be used as reference.

The manufacturer Janssen Cilag, Germany, is responsible for the manufacture of Eprex/ ERYPO® in accordance with the Good Manufacturing Practice (GMP) guidelines.

The solution for injection should be kept in the refrigerator, at a temperature between 2°C and 8°C. The study drugs will be dispensed according to the following diagram:

Medication	Presentation to be dispensed	Titration phase (week 0 to week 12)	Maintenance phase (week 12 to week 24)
HEMAX®	Injectable, 2000 IU/ 0.5ml and 4000 IU/ 0.4 ml in a sufficient amount depending on the dose to be administered.	The initial dose will be 29IU/ kg estimated for an average weight of 70 Kg, what equals to 2000IU twice a week. Dose adjustments will be in aliquots of 25% of the dose that the patient was receiving It is estimated that the mean weekly dose will be 5000 IU ± 2500 IU/ ml. Given that visits are every 2 weeks and that in each visit the medication will be administered at the site, only the necessary amount for the biweekly dose (3 doses) will be dispensed which will not be administered at the site.	The weekly dose will be estimated based on the total dose that the patient was receiving until week 12. That is to say, a patient that was receiving 2000IU/ 0.05 ml twice a week will start to receive 4000IU/ 0.4ml on a weekly basis Dose adjustments will be in aliquots of 25% of the dose that the patient was receiving It is estimated that the mean weekly dose will be similar to the weekly dose administered twice a week. Given that visits are every 4 weeks and that in each visit the medication will be administered at the site, only the necessary amount for the weekly dose (3 doses) will be dispensed which will not be administered at the

site.

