4.4 Study Variables

	V1 Screen	V2 Random	V3	V4	V5	V6	V7	V8	V9	V10	V11 or Final
PROCEDURES - SITE VISITS											
Study weeks	- 1	0	S2	S4	S6	S8	S10	S12	S16	S20	S24
INVESTIGATOR ACTIVITIES											
Obtain the informed consent in writing	X										
Evaluate the inclusion and exclusion	X	X									
Randomization		X									
Blood pregnancy test HCG beta subunit (only in women of childbearing potential)		X	X	X	X	X	X		X	X	
Medical history (with concomitant medication) and physical examination	X										

Blood pressure and pulse	X	X	X	X	X	X	X	X	X	X	X
Electrocardiogram	X										
Complete laboratory test (hemogram; hepatogram; blood glucose; renal function; ionogram; lipids; iron metabolism)	X							X			
Control laboratory test: hemogram			X	X	X	X	X		X	X	
Laboratory measurement of antibodies and hepcidin	X							X			X
Dosing and dose adjustment		X	X	X	X	X	X	X	X	X	
Administration of subcutaneous		X	X	X	X	X	X	X	X	X	
Delivery of medication and dosage record card		X	X	X	X	X	X	X	X	X	
Medication control and dose recording			X	X	X	X	X	X	X	X	X
AEs recording		X	X	X	X	X	X	X	X	X	X

Randomization Visit 2 (Week 0) will be scheduled a week after the baseline screening visit with a window of ± 3 days from the respective date.

The time-window for randomization visit is one week ± 3 days from screening visit.

The time-window for visits 3, 4, 5, 6, and 7 (weeks 2, 4, 6, 8 and 10) is two weeks ± 1 week. The time-window for visits 9, 10 and 11 (weeks 16, 20 and 24) is four weeks ± 1 week.

Adverse events will be recorded from the moment the patient signed the written informed consent, and they will be recorded all the study long. They will be reviewed and updated in each visit, and anytime the patient will be contacted by telephone

5 Sample Size

A total number of 120 patients (60 in each group) will allow, with 80% of power, to rule out a difference between treatment groups greater than 1g/ dl in hemoglobin increase from baseline value to the mean value of the visits between week 8 and 12.

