7.6 Treatment Compliance

The patients should return to the center all the containers with the drug product used during the study, and all the medications that they had not used during the study. The staff in the center recorded in the source document and on the patient accountability individual record, the patient number, and the number of returned containers.

During the study, the monitor checked continuously all the containers with the study medication (used, and non-used containers), and the corresponding accountability forms. At the same time, at each visit the card in which the patient recorded the date and drug product dose administered, is checked. Accountability records of the drug products used during the study were kept in the centers all the time. At the moment the study was ended a final accountability was carried out and all the remnant medication was withdrawn for destruction, as stated in current regulations. .

The following measures will de obtained related to treatment compliance:

- Epoetin dose (IU) administered every week in each group (mean \pm SD): Mean for cumulative doses per patient at the titration stage, maintenance stage, and during the whole treatment
- Number of patients that suspended the treatment at each visit

8 Efficacy Analyses

All efficacy variables will be listed by subject within study site. Data will be summarized by treatment group. Number and percentage will summarize categorical efficacy variables and Number, Mean, Standard Deviation, Minimum and Maximum will summarize continuous efficacy variables, whereas.

Inferential statistics will be performed through intergroup analysis analysis using ANCOVA covariance analysis comparing each treatment group (patients treated with HEMAX PFS versus those treated with EPREX/ ERYPO®) or the statistical “t” Student test for independent samples considering 5% significance level.

An additional intragroup analysis evaluating the variations in hemoglobin (increase from baseline to the average of the visits between weeks 8 and 12) adjusted for the baseline value, using a significance level of 5% will be performed

The assumptions regarding normality and homogeneity will be checked.

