8.1 Primary Efficacy Analysis

The primary efficacy analysis will be performed for Per Protocol population.

The primary efficacy assessment will be carried out through the levels of hemoglobin increase from baseline value to the mean value of the visits between week 8 and 12, comparing patients treated with HEMAX PFS versus those treated with EPREX/ ERYPO®.

Additionally, treatment equivalence will be established if the difference between the two groups excludes a difference between treatment groups greater than 1g/ dl in hemoglobin increase from baseline value to the mean value of the visits between week 8 and 12 with a difference in the mean dose of epoetin alfa in these visits no greater than 20%.

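### The dose condition of the equivalence rule is a cut-off on observed means with no CI, alpha, unit or denominator; taken alone it passes about half the time at a true 20% dose difference

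*SAP*

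**What the plan says.** SAP 3.2.4 sets a two-part rule. The first part is on hemoglobin: "Treatment equivalence will be established if the difference between the two groups excludes a difference between treatment groups greater than 1g/ dl in hemoglobin increase". That change is taken to the average of the week 8 to 12 visits, relative to baseline. The second part is on dose: "with a difference in the mean dose of epoetin alfa in these visits no greater than 20" per cent. SAP 8.1 repeats the dose part ("in these visits no greater than 20" per cent), and the protocol synopsis and section 16.5 carry the same cut-off.

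The formal test is introduced by "The following equivalence statistical hypotheses is to be tested at a two-sided significance level of 5" per cent. Both hypotheses concern the "Treatment difference in mean Hb during the primary efficacy evaluation period, between treatment arms"; dose appears in neither. The sample size statement in SAP section 5 ("A total number of 120 patients (60 in each group) will allow, with 80% of power") refers only to ruling out a 1 g/dl hemoglobin difference.

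None of these places gives the dose condition an interval, a test or an error rate. None states the unit (IU or IU/kg), which arm's mean the 20% is taken of, or how interrupted weeks count. SAP 7.6 lists weekly dose in IU by group, together with the "Mean for cumulative doses per patient at the titration stage, maintenance stage, and during the whole treatment". Protocol 13.5 offers a planning figure for the titration phase: "It is estimated that the mean weekly dose will be 5000 IU ± 2500 IU/ ml". Protocol section 5 gives the same figure per week and attributes it to recent studies.

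**The concern.** The two parts of the rule ask for different kinds of evidence. For hemoglobin, the data must exclude a difference beyond the margin. For dose, two observed averages need only be close enough.

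The asymmetry matters because both arms follow the same hemoglobin-driven titration. Doses go up by 25% for an inadequate rise, down by 25% for a fast rise, and are interrupted at 11.5 g/dl. This pulls the arms' hemoglobin together, at least in part, so a difference in potency would show partly as a difference in dose. The dose condition is the plan's guard against that, and it has no error control.

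The wording also matters downstream. SAP 3.2.4 lets testing move to the secondary endpoints only once equivalence is achieved, and equivalence is defined to include the dose condition.

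**Working it through.** **Inputs.** Planned 60 per arm; enrolled 23 and 20 (SAP section 5). Dose mean 5000 IU/week (Protocol section 5 and 13.5). Reading the ±2500 as an SD is an assumption. It gives a CV of 50%; SD 1500 (CV 30%) is shown as a lower case, and CV 70% was also tried. Hemoglobin SD is not stated.

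**The plan's own figure.** The 120 patients at 80% power cannot be reproduced without an SD. Back-solving two one-sided tests at 60 per arm, margin 1 g/dl and true difference 0 gives an SD of 1.69 g/dl (95% CI) or 1.87 g/dl (90% CI). Check of the first: SE = 1.69 × √(1/60 + 1/60) = 0.309; (1/0.309) − 1.96 = 1.28; 2Φ(1.28) − 1 = 0.80.

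**Dose condition alone.** With true relative difference d and SE = CV × √(1/n1 + 1/n2):

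P(pass) = Φ((0.20 − d)/SE) − Φ((−0.20 − d)/SE)

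- 23/20: √(1/23 + 1/20) = 0.3057, so SE = 9.2% of the mean (SD 1500) or 15.3% (SD 2500).
- 60/60: √(1/60 + 1/60) = 0.1826, so SE = 5.5% or 9.1%.

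| True difference | 60/60, SD 1500 | 60/60, SD 2500 | 23/20, SD 1500 | 23/20, SD 2500 |
|---|---|---|---|---|
| 0% | 100% | 97% | 97% | 81% |
| 20% | 50% | 50% | 50% | 50% |
| 25% | 18% | 29% | 29% | 37% |
| 30% | 3% | 14% | 14% | 26% |

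At d = 20% the first term is Φ(0) = 0.5 whatever the SE. The second term is negligible here; at CV 70% and 23/20 it lowers the rate to 46.9%. The formula treats the denominator as fixed. Simulating ratios of gamma-distributed means gave 49.5% to 50.2%, and about 47% at CV 70% with 23/20.

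**Both conditions together.** True dose difference 20%, true hemoglobin difference 0, dose CV 50%. At the stated 80% hemoglobin power and 60 per arm, 0.80 × 0.50 = 40%. Simulated joint pass rates:

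| Hemoglobin SD (assumed) | 60/60, 95% CI | 60/60, 90% CI | 23/20, 95% CI | 23/20, 90% CI |
|---|---|---|---|---|
| 1.0 | 50% | 50% | 40% | 45% |
| 1.25 | 49% | 50% | 24% | 33% |
| 1.69 | 40% | 44% | 0% | 11% |

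The zero arises because 1.96 × 1.69 × 0.3057 = 1.01 g/dl, already wider than the margin. Correlations between the two estimates of −0.5, 0 and 0.5 changed the rates by less than one point.

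**What an interval would show at 23/20.** Half-width = t(41 df) × SE. For 90%: 1.683 × 9.17% = 15.4% (SD 1500) and 1.683 × 15.29% = 25.7% (SD 2500). For 95%: 2.02 × 9.17% = 18.5% and 2.02 × 15.29% = 30.9%. With truly equal doses, the chance that the interval lies within ±20% is about 41% (90% CI) or 17% (95% CI) at SD 1500, and zero at SD 2500.

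**The case against.** **The 50% is a ceiling for the declaration.** A reader might infer that equivalence as a whole is falsely declared half the time. The documents do not support that: hemoglobin must pass too. Half is also what any point-estimate cut-off gives at its own boundary. Both statements stand. The 50% describes the dose condition; the joint rates above describe the declaration.

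**The unit is unstated rather than wrong.** A reader might infer from SAP 7.6 that the rule runs on unscaled IU and that the weeks 8-12 dose is never produced. SAP 7.6 is a compliance summary and does not define the rule. It lists weekly dose by group, from which the weeks 8-12 mean can be derived. The supportable point is that unit and denominator are missing.

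**Weight imbalance does not add to the SE.** An SD in IU already contains between-patient weight variation. If weight SD is 12 to 18 kg on 70 kg (an assumption), its share is 5% to 8% of the mean, and removing it would lower 15.3% only to about 13% to 14%. Stratifying by sex may balance some of it.

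**SD 2500 is a high assumption.** At 70 kg the start is 4000 IU/week, and two 25% increases cap it at 4000 × 1.25² = 6250. With mean 5000 and range 0 to 6250, the largest possible SD is √(5000 × 1250) = 2500. Varying weights relax that bound, but the objection is fair, so results are given as a range.

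**Changing a protocol success rule late.** Requiring the dose CI to lie within 20% for success, after recruitment ended and an interim look, would be debatable. At CV 50% it would need 108 (90% CI) or 132 (95% CI) per arm for 80% power. This stands, and the fix therefore narrows the claim and does not impose that test.

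**Could the exclusion wording also govern dose?** The sentence structure and the hypotheses point to hemoglobin only. If the sponsor means otherwise, the text still has to say so.

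**Conclusion.** The concern holds for the dose condition. It is a comparison of observed means without error control, and it passes about 50% of the time at a true 20% difference, almost whatever the sample size or SD. The joint rate with hemoglobin is about 40% at 60/60 and the stated power. At 23/20 it is about 0% to 45%, and it is low only where the hemoglobin condition itself rarely passes. At 23/20, a true 30% difference passes the dose condition 14% to 26% of the time, while equal products pass 97% to 81% (SD 1500 to 2500).

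These figures assume a mean of 5000 IU/week, the SDs shown, no true hemoglobin difference in the joint calculation, and all enrolled patients analysed. SAP 8.1 uses the per-protocol population, so fewer may contribute. The stated 80% power says nothing about dose. As written, meeting the rule would not be controlled evidence that the products need similar doses.

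**What to change.** In SAP 3.2.4 and 8.1:

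1. Define the weeks 8-12 dose measure: the unit, the EPREX/ERYPO mean as denominator, and interrupted weeks counted as zero. Report IU/kg by baseline weight alongside IU.
2. Report the percentage difference between arms with its CI, at a level reconciled with the stated two-sided 5%.
3. Label the 20% point-estimate check descriptive, restrict the word equivalence to hemoglobin, and state that dose equivalence is not shown unless the CI lies within ±20%.
4. State that the 80% power applies to hemoglobin alone, and which condition opens the step-down to secondary endpoints.

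The two-part rule also stands in the protocol synopsis and 16.5, and making the dose check descriptive removes a hurdle. The SAP should therefore record the departure and still print whether the 20% check was met.

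The cost is SAP wording and one estimate from recorded doses and baseline weight; no new data are needed. The downside is that with 43 patients the dose comparison may read as inconclusive, and almost certainly will if the SD is near 2500.
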